5.1.1 Administrative Procedures

5.1.1.1 Informed Consent

The Investigator will make certain that an appropriate informed consent process is in place to ensure that potential research subjects, or their authorized representatives, are fully informed about the nature and objectives of the clinical study, the potential risks and benefits of study participation, and their rights as research subjects. The Investigator, or a sub-investigator(s) designated by the Investigator, will obtain the written, signed informed consent of each subject, prior to performing any study-specific procedures on the subject. The date and time that the subject, or the subject's authorized representative, signs the informed consent form and a narrative of the issues discussed during the informed consent process will be documented in the subject's case history. The Investigator will retain the original copy of the signed informed consent form, and a copy will be provided to the subject, or to the subject's authorized representative.

The Investigator will make certain that appropriate processes and procedures are in place to ensure that ongoing questions and concerns of enrolled subjects are adequately addressed and that the subjects are informed of any new information that may affect their decision to continue participation in the clinical study. In the event of substantial changes to the clinical study or the risk-to-benefit ratio of study participation, the Investigator will obtain the informed consent of enrolled subjects for continued participation in the clinical study.

5.1.1.2 Inclusion/Exclusion Criteria

All inclusion and exclusion criteria will be reviewed by the investigator or qualified designee to ensure that the subject qualifies for the trial.

5.1.1.3 Medical History

A medical history will be obtained by the investigator or qualified designee. Medical history will include all active conditions, and any condition diagnosed within the prior 10 years that are considered to be clinically significant by the Investigator.

5.1.1.4 Concomitant Medications Review

The investigator or qualified designee will record medication, if any, taken by the subject during the trial. All medications related to reportable SAEs and ECIs should be recorded as defined in Section 7.2.

Concomitant medications will stop being collected at the time of starting a new anti-cancer therapy.

5.1.1.5 Disease Details and Treatments

5.1.1.5.1 Disease Details

The investigator or qualified designee will obtain prior and current details regarding disease status.

5.1.1.5.2 Prior Treatment Details

The investigator or qualified designee will review all prior cancer treatments including systemic treatments, radiation and surgeries.

5.1.1.6 Assignment of Screening Number

Screening numbers will be assigned by sequential numbering.

5.1.1.7 Assignment of Treatment Number

Treatment numbers will be assigned by sequential numbering.

5.1.1.8 Trial Compliance (Medication/Diet/Activity/Other)

Axitinib pills will be counted at each monthly visit.

5.1.2 Clinical Procedures/Assessments

Patients will undergo study treatments and evaluation at the UPMC-Hillman Cancer Center. Patients will continue to be evaluated every 12 weeks (+/- 1 week) with scans, labs and MD visit.

5.1.2.1 Adverse Event (AE) Monitoring

The investigator or qualified designee will assess each subject to evaluate for potential new or worsening AEs as specified in the Trial Flow Chart and more frequently if clinically indicated. Adverse experiences will be graded and recorded throughout the study and during the follow-up period according to NCI CTCAE Version 5.0 (see Section 11.2). Toxicities will be characterized in terms regarding seriousness, causality, toxicity grading, and action taken with regard to trial treatment.

Please refer to section 7.2 for detailed information regarding the assessment and recording of AEs.

5.1.2.2 Full Physical Exam

The investigator or qualified designee will perform a complete physical exam during the screening period. Clinically significant abnormal findings should be recorded as medical history.

5.1.2.3 Vital Signs

The investigator or qualified designee will take vital signs at screening, prior to the administration of each dose of trial treatment and at treatment discontinuation as specified in the Trial Flow Chart (Section 5.0). Vital signs should include temperature, pulse, respiratory rate, weight and blood pressure. Height will be measured at screening only.

5.1.2.4 Eastern Cooperative Oncology Group (ECOG) Performance Scale

The investigator or qualified designee will assess ECOG status (see Section 11.1) at screening, prior to the administration of each dose of trial treatment and discontinuation of trial treatment as specified in the Trial Flow Chart.

5.1.2.5 Tumor Imaging and Assessment of Disease

PET/CT and CT

- -At baseline and week 12, extra-cranial tumor assessment will be conducted with contrast-enhanced PET/CT or CT and applied using RECIST 1.1 criteria.
- -A screening scan will be performed prior to enrollment unless a recent (within 28 days of enrollment) scan is available. Target and non-target lesions must be identified at time of screening scan and the same lesions must be re-assessed at each restaging scan.
- -Repeat PET/CT or CT imaging will be obtained at week 12, and then CT will be obtained at 12 week intervals.
- -Complete response/partial response confirmation assessments must take place at least 4 and up to 12 weeks after the documentation of initial response. If the last radiographic assessment for extra-cranial disease was more than 8 weeks prior to discontinuation from study and progressive disease has not been documented, disease assessment should be obtained at the time of study discontinuation.
- -If patients have PD by RECIST 1.1 criteria, the Immune Related Response Criteria (irRC) will be used for assessment of tumor response for the purposes of managing patients on protocol treatment and decision making for discontinuation of study therapy due to disease progression. These disease assessments will be performed by the investigator with site radiology reading.
- For the purposes of the secondary efficacy endpoint of the study, response assessment based on RECIST 1.1 will be applied as the primary measure and irRC by investigators will be evaluated as a secondary assessment only if patient have PD by RECIST 1.1. If patients have PD by RECIST 1.1 but have SD or PR by irRC, they will be permitted to continue treatment. In order for a patient to continue to receive study treatment beyond progression by RECIST 1.1, in addition to having SD or PR by irRC, patients must not have symptoms or signs of disease progression, including significantly worse laboratory values or a decline in ECOG performance status.
- At the time of radiographic progression of disease, if treatment is to continue beyond PD, patients will be re-consented and adequately informed of all FDA-approved therapy, and potential clinical benefit, that the patient may be foregoing in order to continue receiving the investigational product.

MRI

Intra-cranial tumor assessments will be conducted with contrast-enhanced MRI. A screening scan will be performed prior to enrollment unless a recent (within 4 weeks of enrollment) scan is available. If brain metastases are known or identified at screening, brain imaging should be repeated at 12 weeks or as it is standard, unless acute neurological symptoms develop. If no brain metastases are known or identified at pre-study imaging, no brain imaging need be performed following pre-study assessment unless acute neurological symptoms develop. CT scans of the brain can be utilized if MRI cannot be obtained in a timely manner per the treating physician.

5.1.2.6 Tumor Tissue Collection and Correlative Studies Blood Sampling

Patients will have blood drawn for correlative studies at baseline (up to 30 days prior to treatment initiation), at week 12 (+/- 3 days) study flow chart says +/- 7 days, which is correct?, and at progression. This includes 10 green top tubes, 2 red top tubes and an ACD yellow top tube (yellow top at baseline only). Refer to lab manual for full details.

Patients will undergo biopsy for tumor tissue collection at baseline (up to 30 days prior to treatment initiation) and at week 12 (+/- 7 days). A biopsy at time of progression is optional. Refer to lab manual for full details.

5.1.3 Laboratory Procedures/Assessments

Details regarding specific laboratory procedures/assessments to be performed in this trial are provided below.

Laboratory Safety Evaluations (Hematology, Chemistry and Urinalysis): Laboratory tests for hematology, chemistry, urinalysis, and others are specified in Table 7.

Table 7: Laboratory Tests

Hematology	Chemistry	Other
Hematocrit	Albumin	Serum β-human chorionic gonadotropin†
Hemoglobin	Alkaline phosphatase	(β-hCG)†
Platelet count	Alanine aminotransferase (ALT)	Free thyroxine (T4)
WBC (total and differential)	Aspartate aminotransferase (AST)	Thyroid stimulating hormone (TSH)
Absolute Neutrophil Count	Lactate dehydrogenase (LDH)	
	Calcium	
	Chloride	Blood for correlative studies
	Glucose	
	Potassium	
	Sodium	
	Phosphorous	
	Total Bilirubin	
	Direct Bilirubin (If total bilirubin is elevated above the upper limit of normal)	
	Total protein	
	Blood Urea Nitrogen	
	СРК	
† Perform on women of childbearing potential only. If urine pregnancy results cannot be confirmed as negative, a serum pregnancy test will be required.		

5.1.4 Other Procedures

5.1.4.1 Withdrawal/Discontinuation

When a subject discontinues/withdraws prior to trial completion, all applicable activities scheduled for the final trial visit should be performed at the time of discontinuation. Any adverse events which are present at the time of discontinuation/withdrawal should be followed in accordance with the safety requirements outlined in Section 7.2 - Assessing and Recording Adverse Events. Subjects who a) attain a CR or b) complete 24 months of treatment with nivolumab may discontinue treatment.

5.1.5 Visit Requirements

Visit requirements are outlined in Section 5.0 - Trial Flow Chart. Specific procedure-related details are provided above in Section 6.0 - Trial Procedures.

5.2 Assessing and Recording Adverse Events

An adverse event is defined as any untoward medical occurrence in a patient or clinical investigation subject administered a pharmaceutical product and which does not necessarily have to have a causal relationship with this treatment. An adverse event can therefore be any unfavorable and unintended sign (including an abnormal laboratory finding, for example), symptom, or disease temporally associated with the use of a medicinal product or protocol-specified procedure, whether or not considered related to the medicinal product or protocol-specified procedure. Any worsening (i.e., any clinically significant adverse change in frequency and/or intensity) of a preexisting condition that is temporally associated with the use of the treatments agents, is also an adverse event.

All adverse events that occur after the consent form is signed but before treatment allocation/randomization must be reported by the investigator if they cause the subject to be excluded from the trial, or are the result of a protocol-specified intervention, including but not limited to washout or discontinuation of usual therapy, diet, placebo treatment or a procedure.

From the time of treatment allocation/randomization through 100 days following cessation of treatment, or until the participant initiates new anticancer therapy, whichever is earlier, all adverse events must be reported by the investigator. Such events will be recorded at each examination on the Adverse Event case report forms/worksheets. The reporting timeframe for adverse events meeting any serious criteria is described in section 7.2.3.1. The investigator will make every attempt to follow all subjects with non-serious adverse events for outcome.

Adverse events will not be collected for subjects during the pre-screening period (for determination of archival tissue status) as long as that subject has not undergone any protocol-specified procedure or intervention. If the subject requires a blood draw, fresh tumor biopsy etc., the subject is first required to provide consent to the main study and AEs will be captured according to guidelines for standard AE reporting.

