4.2.5 Timing of Dose Administration

Nivolumab: Trial treatment should be administered on Day 1 of each cycle after all procedures/assessments have been completed as detailed on the Trial Flow Chart (Section 6.0). Trial treatment may be administered up to 3 days before or after the scheduled Day 1 of each cycle due to administrative reasons.

All trial treatments will be administered on an outpatient basis.

Nivolumab 480 mg will be administered as a 30 minute IV infusion every 4 weeks. Sites should make every effort to target infusion timing to be as close to 30 minutes as possible. However, given the variability of infusion pumps from site to site, a window of -5 minutes and +10 minutes is permitted (i.e., infusion time is 30 minutes: -5 min/+10 min).

Nivolumab will be prepared and infused per institutional standards

Axitinib: Axitinib 5 mg PO twice daily, 12 hours apart, will be taken for the entire duration of treatment. Patients will be given specific instructions on how to take axitinib. If a dose is missed, it may be taken up to 8 hours later that same day.

Dosing interruptions of nivolumab and axitinib are permitted in the case of medical / surgical events or logistical reasons not related to study therapy (e.g., elective surgery, unrelated medical events, patient vacation, and/or holidays). Subjects should be placed back on study therapy within 3 weeks of the scheduled interruption, unless otherwise discussed with the Sponsor. The reason for interruption should be documented in the patient's study record.

Should the combination of nivolumab and axitinib be further investigated for the treatment of anti-PD1 refractory melanoma, given the potential for late onset immune-related toxicities for nivolumab, any such late toxicity will be considered in the determination of the final dose and dose schedule. The number of required dose reductions of axitinib will also be taken into full consideration.

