4.5 Subject Withdrawal/Discontinuation Criteria

Subjects may withdraw consent at any time for any reason or be dropped from the trial at the discretion of the investigator should any untoward effect occur. In addition, a subject may be withdrawn by the investigator or the Sponsor if enrollment into the trial is inappropriate, the trial plan is violated, or for administrative and/or other safety reasons.

A subject must be discontinued from the trial for any of the following reasons:

- The subject or legal representative (such as a parent or legal guardian) withdraws consent.
- Confirmed radiographic disease progression

Note: For unconfirmed radiographic disease progression, please see Section 5.2.2

Note: A subject may be granted an exception to continue on treatment with confirmed radiographic progression if clinically stable or clinically improved, please see Section 7.1.2.7.1

- Unacceptable adverse experiences as described in Section 5.2.1.2
- Intercurrent illness that prevents further administration of treatment
- Investigator's decision to withdraw the subject
- The subject has a confirmed positive serum pregnancy test
- Noncompliance with trial treatment or procedure requirements
- The subject is lost to follow-up
- Completed 24 months of uninterrupted treatment with nivolumab or 24 administrations of study medication, whichever is later.

Note: 24 months of study medication is calculated from the date of first dose.

• After trial discontinuation (whether due to subject withdrawal, progression, or dose limiting toxicity), patients will be seen at week 4 for follow up, and then followed once 100 days after the last day of treatment even if they start a new anticancer therapy. Patients will be contacted by phone for survival follow up for up to 5 years.

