5.0 TRIAL PROCEDURES

5.1 Study Flow Chart

	Baseline*	C1 +/-3 days	C2 +/-3 day	C3 +/-3 day	C4 +/-3 day	C5 +/-3 day	C6 +/-3 day	C7 +/-3 day	C8 +/-3 day	C9 +/-3 day	C10 +/-3 day	C11 +/-3 day	C12 + +/-3 day	ЕОТ	Follow up#
Informed consent	X														
Demographics	X														
Medical history	X														
Concurrent meds	X	XX									X	Х			
Physical exam	X	X	XX										X	X	
Vital signs	X	X	XX										X	X	
Performance status (ECOG)	X	XX											X	X	
CBC w/diff, plts	X	X	X	X	X	X	X	X	X	X	X	X	X	X	X
Serum chemistry ^a	X	X	X	X	X	X	X	X	X	X	X	X	X	X	X
Urine dipstick	X			х		х		х		х		Х		х	
Adverse event evaluation		XX									X	X			
Radiologic evaluation & Tumor measurements	Х	Tumor measurements will be evaluated with the first scans at week 12 (+/- 1 week). Subsequent scans will be repeated every 12 weeks (+/- 1 week). Patients with complete or partial response will have confirmation scans at least 4 and up to 12 weeks later. Documentation (radiologic) must be provided for patients removed from study for progressive disease. Brain MRI will be obtained at baseline, and will be repeated at 12 weeks if patients have known brain mets, or develop neurological symptoms**. CT scans of the brain can be utilized if MRI cannot be obtained in a timely manner per the treating physician.										Х			
B-HCG ^b	X	XX													
TSH, free T4 ^c	X		X		X		X		X		X		X	X	

Tumor bx ^d	X				X										
Research Blood draws ^e	X				X									X	
Axitinib administration ^f		X	X	X	X	X	X	X	X	X	X	X	X		
Nivolumab administration		X	X	X	X	X	X	X	X	X	X	X	X		
Microbiome sampling g	X				X							X		X	

^{*:} Baseline is within 30 days of start of treatment, except for labs (14 days).

- #: After trial discontinuation (whether due to subject withdrawal, progression, or dose limiting toxicity), patients will be seen at week 4 for follow up. Survival follow-up will be obtained at day 100 days after the last day of treatment (this can be done by phone), even if they start a new anticancer therapy. Patients will be contacted by phone for survival follow up for up to 5 years.
- **: If known to have prior brain metastases, must not have evidence of active (enlarging and/or symptomatic lesions) brain disease on MRI evaluation within 2 weeks from SRS or WBRT treatment. CT scans of the brain can be utilized if MRI cannot be obtained in a timely manner per the treating physician at baseline and also at 2 week follow up, if asymptomatic.

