The Sponsor will reconcile the clinical database SAE cases (case level only) transmitted to BMS Global Pharmacovigilance ([contact]). Frequency of reconciliation should be every 3 months and prior to the database lock or final data summary. BMS GPV&E will email, upon request from the Investigator, the GPV&E reconciliation report. Requests for reconciliation should be sent to [contact]. The data elements listed on the GPV&E reconciliation report will be used for case identification purposes. If the Investigator determines a case was not transmitted to BMS GPV&E, the case should be sent immediately to BMS.

Refer to Table 3 in Section 4.2.4 for additional details regarding each of the above criteria.

For the time period following the subject's written consent to participate in the study through 100 days of discontinuation of dosing, any serious adverse event, or follow up to a serious adverse event, including death due to any cause other than progression of the cancer under study (reference Section 7.2.3.3 for additional details) that occurs to any subject must be reported within 24 hours to the Sponsor and within 24 hours or 1 business day to BMS and Pfizer Global Safety if it causes the subject to be excluded from the trial, or is the result of a protocol-specified intervention, including but not limited to washout or discontinuation of usual therapy, treatment or a procedure.

For the time period beginning at treatment allocation/randomization through 100 days following cessation of treatment with nivolumab, or until the participant initiates new anticancer therapy, whichever is earlier, any serious adverse event, or follow up to a serious adverse event, including death due to any cause other than progression of the cancer under study (reference Section 7.2.3.3 for additional details), whether or not related to study treatment, must be reported within 24 hours to the Sponsor and within 24 hours or 1 business day to BMS and Pfizer Global Safety.

Additionally, any serious adverse event, considered by an investigator who is a qualified physician to be related to treatment that is brought to the attention of the investigator at any time following consent through the end of the specified safety follow-up period specified in the paragraph above, or at any time outside of the time period specified in the previous paragraph also must be reported immediately to the Sponsor and to BMS and Pfizer Global Safety.

REPORTING OF SERIOUS ADVERSE EVENTS

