5.2.2.2 Events of Clinical Interest

Selected non-serious and serious adverse events are also known as Events of Clinical Interest (ECI) and must be reported within 24 hours to the Sponsor and within 2 working days to BMS Global Safety.

For the time period beginning when the consent form is signed until treatment allocation/randomization, any ECI, or follow up to an ECI, that occurs to any subject must be

reported within 24 hours to the Sponsor and within 24 hours/1 business day to BMS and Pfizer Global Safety if it causes the subject to be excluded from the trial, or is the result of a protocol-specified intervention, including but not limited to washout or discontinuation of usual therapy, diet, placebo treatment or a procedure.

For the time period beginning at treatment allocation/randomization through 100 days following cessation of treatment, or 30 days following cessation of treatment if the subject initiates new anticancer therapy, whichever is earlier, any ECI, or follow up to an ECI, whether or not related to treatment, must be reported within 24 hours to the Sponsor and within 24 hours to BMS and Pfizer Global Safety.

Events of clinical interest for this trial include:

- 1. An overdose of nivolumab or axitinib, as defined in Section 7.2.1 Definition of an Overdose for This Protocol and Reporting of Overdose to the Sponsor, that is not associated with clinical symptoms or abnormal laboratory results.
- 2. An elevated AST or ALT lab value that is greater than or equal to 3X the upper limit of normal and an elevated total bilirubin lab value that is greater than or equal to 2X the upper limit of normal and, at the same time, an alkaline phosphatase lab value that is less than 2X the upper limit of normal, as determined by way of protocol-specified laboratory testing or unscheduled laboratory testing.*

*Note: These criteria are based upon available regulatory guidance documents. The purpose of the criteria is to specify a threshold of abnormal hepatic tests that may require an additional evaluation for an underlying etiology.

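### The safety-collection windows disagree, and new non-serious adverse events, including related Grade 3 events, are not collected once a patient starts new anticancer therapy

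*Combined protocol and SAP*

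**What the plan says.** The combined protocol and SAP sets the post-treatment safety window in several places.

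- **All adverse events (5.2):** reported "through 100 days following cessation of treatment, or until the participant initiates new anticancer therapy, whichever is earlier, all adverse events must be reported".
- **Serious adverse events, related or not (5.2.2.1):** "through 100 days following cessation of treatment with nivolumab, or until the participant initiates new anticancer therapy, whichever is earlier, any serious adverse event". The clock here starts when nivolumab stops. A preceding paragraph gives a narrower set (events that exclude the patient or result from a protocol intervention) 100 days with no cut-off at new therapy.
- **Related serious adverse events (5.2.2.1):** "any serious adverse event, considered by an investigator who is a qualified physician to be related to treatment" and brought to the investigator's attention is reportable within the window, "or at any time outside of the time period specified in the previous paragraph also must be reported immediately to the Sponsor".
- **Events of clinical interest (5.2.2.2):** 100 days, "or 30 days following cessation of treatment if the subject initiates new anticancer therapy, whichever is earlier, any ECI". The two listed events are an overdose without symptoms or abnormal results and a combined transaminase, bilirubin and alkaline phosphatase criterion.
- **Safety analysis (6.4.3):** adverse events are recorded up to 28 days after the last intake of study medication, with no distinction by new therapy.
- **Adverse event monitoring (5.1.2.1):** events are graded and recorded during the study and in follow-up; no end day is given.

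Contact with the patient continues after a switch. Under 4.5, patients are seen at week 4 and then "followed once 100 days after the last day of treatment even if they start a new anticancer therapy". Footnote # of the flow chart (5.1) describes the later contact this way: "Survival follow-up will be obtained at day 100 days after the last day of treatment (this can be done by phone").

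Section 4.2.4.1 warns that nivolumab toxicity may appear several months after the last dose. Section 4.2.5 says that, if the combination is studied further, "given the potential for late onset immune-related toxicities for nivolumab, any such late toxicity will be considered in the determination" of the final dose and schedule.

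**The concern.** Two problems arise together.

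First, the sections give different answers to how long adverse events are collected. A site following 5.2 and an analyst following 6.4.3 would work from different data.

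Second, the 5.2 cut-off depends on the patient's course. Patients who switch early have a short observation period and those who do not switch have a longer one, so under-counting of late toxicity would fall on patients who leave for other treatment. Those patients stay in the denominator of the safety summaries and of the 6.2 monitoring rule. That rule counts Grade 3 or higher toxicity attributable to the combination, which need not be serious in the regulatory sense, and it states no observation window of its own. The protocol expects late immune toxicity and intends to use it, so the events that can drop out are ones it wants to know about.

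**Working it through.** This is mainly a comparison of passages. Days are counted from the end of treatment. Take one patient who switches on day 14 and one who does not.

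| Section | Events | Window ends, no switch | Window ends, switch on day 14 |
|---|---|---|---|
| 5.2 | All adverse events | Day 100 | Day 14 |
| 5.2.2.1 | Serious, regardless of cause | Day 100 (from nivolumab) | Day 14 |
| 5.2.2.1 | Serious and related | No limit, if brought to attention | No limit, if brought to attention |
| 5.2.2.2 | Events of clinical interest | Day 100 | Day 30 |
| 6.4.3 | All adverse events | Day 28 | Day 28 |
| 5.1.2.1 | Adverse events | Follow-up, no day given | Follow-up, no day given |

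Test events against the table:

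1. *Switch on day 14, new non-serious related Grade 3 event on day 40.* It is outside 5.2 (closed day 14), not a serious event, past the 30-day limit in 5.2.2.2, and outside 6.4.3 (closed day 28). No dated window covers it. Only the general sentence in 5.1.2.1 might.
2. *Switch on day 14, qualifying liver abnormality on day 25.* It is outside 5.2 but reportable under 5.2.2.2 and inside 6.4.3. It is captured, though the sections disagree on whether it is a recorded adverse event.
3. *Switch on day 14, related serious event on day 60.* Reportable under 5.2.2.1. Not lost by rule.
4. *Switch on day 14, serious event judged unrelated on day 40.* In general not required.
5. *No switch, non-serious event on day 40.* Inside 5.2, outside 6.4.3. For these patients the two sections differ over 100 − 28 = 72 days.

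**Number of patients affected.** The documents give no rate of progression or switching. Section 6.3 gives only response rates: with 31 patients, 31 × 0.90 = 27.9 non-responders at 10% and 31 × 0.75 = 23.25 at 25%. Non-response is not switching: it includes stable disease, and 5.1.2.5 allows treatment beyond progression under conditions.

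**Sensitivity of the 6.2 rule (illustration).** The plan's own figures come first. With a Beta(1,1) prior, the boundary is the smallest x for which Pr(rate > 0.30 | Beta(1+x, 1+n−x)) ≥ 0.7, and this matches every row of the table in 6.2. An exact patient-by-patient recursion from 3 to 31 patients gives stopping probabilities of 0.10, 0.37, 0.71 and 0.93 at true rates 0.1, 0.2, 0.3 and 0.4, as stated. Now assume that a share m of counted events is not captured, so the observed rate is 0.30 × (1 − m):

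| m (assumed) | Observed rate | Stopping probability |
|---|---|---|
| 0 | 0.300 | 0.71 |
| 5% | 0.285 | 0.66 |
| 10% | 0.270 | 0.61 |
| 20% | 0.240 | 0.51 |
| 30% | 0.210 | 0.40 |

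Nothing in the documents fixes m. Because related serious events remain reportable, only non-serious related Grade 3 events that begin after a switch contribute to the loss from this cut-off. The calculation also treats each event as known before the next patient enters, which late events often would not be.

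**The case against.** The best defence has four parts.

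- **Ending routine collection at new therapy is defensible.** Attribution becomes harder, and 5.1.1.4 stops concomitant medication collection at the same moment. This stands as a reason not to collect everything after a switch. It is not a reason to drop events the investigator considers related.
- **Different event classes may have different windows.** True in general, but 5.2 and 6.4.3 give different windows for the same class.
- **The gap is narrow.** A reader might infer that serious event collection closes at a switch and late immune toxicity is lost. The documents do not support that. Related serious events are reportable at any time, Grade 4 is defined by life-threatening consequences (Table 8) and so meets a serious criterion, and events present at discontinuation are followed (5.1.4.1). This stands, although reporting outside the window depends on the event reaching the investigator.
- **Follow-up may already include an adverse event enquiry.** A reader might conclude that nobody is asked about adverse events between week 4 and day 100. The adverse event row of the flow chart is too broken in the available text to show that, and 5.1.2.1 refers to recording in follow-up. What can be said is that footnote # describes the day-100 contact only as survival follow-up.

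It is also fair that 4.2.5 is conditional on further development and promises only to consider late toxicity.

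**Conclusion.** The concern holds in a limited form. The windows in 5.1.2.1, 5.2, 5.2.2.1, 5.2.2.2 and 6.4.3 are not consistent. Under 5.2, new non-serious adverse events that begin after a switch are not collected, including related Grade 3 events that belong in the safety endpoint and the 6.2 count. Serious events judged unrelated generally drop out as well. Related serious toxicity does not.

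The size cannot be derived. One could assume that 50% to 80% of patients switch at 2 to 6 weeks and obtain an average of 0.5 × (100 − 42) = 29 to 0.8 × (100 − 14) = 68.8 days lost per patient. That should not be read as an estimate: the switching share and timing are invented, the result counts calendar days rather than events, and related serious events stay reportable throughout. The 6.2 figures above likewise show sensitivity, not an expected loss.

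This is a worthwhile, inexpensive improvement, not a flaw that undermines the trial.

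**What to change.** Reconcile 5.1.2.1, 5.2, 5.2.2.1, 5.2.2.2 and 6.4.3 into one window, with one stated starting point:

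- All adverse events to day 100 or the start of new anticancer therapy, whichever comes first.
- After that, events at least possibly related to nivolumab or axitinib, and events of clinical interest, through day 100 whether or not new therapy has started.
- Related serious events reportable at any time, as now.
- The new therapy and its start date recorded, with 5.1.1.4 adjusted to allow this.

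State in 4.5 and flow-chart footnote # that the existing day-100 contact includes an adverse event enquiry as well as the survival check. In 6.4.3, replace the 28-day limit with the common window and summarise events before and after the switch separately.

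The cost is an amendment to the wording, a few questions at a contact already planned, and the recording of new therapy. The downside is less certain attribution after a switch. Restricting collection to at-least-possibly-related events and reporting the two periods separately handles this reasonably well, but does not remove it.
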